2.3 Safety parameters, adverse events and concurrent illnesses

The key safety parameters are the serious and significant adverse events listed in Appendix A (adverse events are classified as 'serious', 'significant' or 'non-significant'). Clinical assessment is made at the study visit(s) for these parameters. The presence of any adverse event will be reported on the case report forms and described in the final report. Similarly, any concurrent illness that is likely to impact on the relevance and quality of the captured data will be noted on the case report form.

2.3.1 Investigator obligations

At all times the investigator will act in the best interest of the subject. Referral or treatment of an adverse event or other clinical finding should be initiated in the best clinical judgement of the investigator, irrespective of the participation in the clinical study.

2.3.2 Reporting obligations

In the case of a 'serious' or 'significant' adverse event, the Principal Investigator will notify the Industrial Contact Person as soon as possible. [REDACTED] and any regulatory authorities will be informed as required.

2.4 Study termination

If it becomes necessary to terminate the study earlier than planned, the Industrial Contact Person will notify the Principal Investigator who will end the study with the cooperation of other staff members. [REDACTED]

2.5 Protocol deviations

Any deviations from this protocol will be recorded and reported to the Industrial Contact Person as appropriate. [REDACTED]

2.5.1 Protocol amendments

Any amendments will be agreed between the Industrial Contact Person and the Principal Investigator with the cooperation of other staff members. Amendments will be recorded, identified and distributed. [REDACTED]

[REDACTED]

2.6 Study resources

Study products will be stored according to the manufacturer's product instructions.

2.6.1 Lenses

Details of the study lenses are provided in Table 2. The Proclear Toric XR Multifocal lens is currently CE marked and the Biofinity XR Toric Multifocal lens is currently undergoing CE marking. The study will not commence until this lens has CE approval. Initial lens selection will be as indicated by the manufacturers' fitting guidelines.

	Test lens	Control lens
Name	Biofinity XR Toric Multifocal	Proclear Toric XR Multifocal
Manufacturer	CooperVision	CooperVision
Material	Comfilcon A	Omafilcon B
EWC (%)	48%	62%
Base Curve (mm)	8.7	8.4 / 8.8
Diameter (mm)	14.5	14.4
Spherical powers (DS)	+10.00 to -10.00 (0.50 steps after $\pm 6.50D$)	+20.00 to -20.00 (0.50 steps after -6.50D)
Cyl Powers (DC)	-0.75 to -5.75 (0.50 steps)	-0.75 to -5.75 (0.50 steps)
Axis	5 to 180 (5 degree steps)	5 to 180 (5 degree steps)
Add	+1.00 to +4.00 (D & N)	+1.00 to +4.00 (D & N)

Table 2: Study lenses.

2.6.1.1 Use of lenses

All lens types will be worn on a daily wear basis. Lenses should be worn for a minimum of six hours per day, five days per week. The lenses should also be worn for a minimum of two hours before attending the follow-up visits.

2.6.2 Care regimen

Subjects will use Synergi (CooperVision Inc.) Multi-Purpose Solution including a 'rub and rinse' step. Subjects can also use comfort/lubricating drops (Blink Contacts manufactured by AMO) if this is necessary.

2.6.3 Inventory control

CooperVision Inc. will supply both lens types and the lens care system. [REDACTED]

[REDACTED] will supply any comfort/lubricating drops.

All worn lenses will be discarded. Unworn lenses will be retained [REDACTED]
[REDACTED]

2.6.4 Clinical equipment

Clinical equipment is regularly maintained and calibrated as required. Standard operating procedures and international standards are used where appropriate.

2.7 Study control

This study is controlled by cross-comparison. Bias will be minimised by randomising the order of assessment.

2.8 Documentation

Documents related to this work that require archiving will be kept [REDACTED] for a period of 10 years after completion of the final report. The Sponsor's permission will be sought before the documents are destroyed.

2.9 Data collection and analysis

Data collected in this work will be recorded on a custom-developed database and an established data trail. Data handling will include export of the study information from the clinical database into spreadsheet format for manipulation, followed by export into a statistical package for analysis. Most clinical data will be entered directly onto the electronic case report form and is considered to be source data.

2.10 Study completion

The clinical phase of the study will be considered complete when all subjects have signed the exit statement.

2.11 Confidentiality

All matters related to this work will remain confidential within [REDACTED], the funding company and any regulatory authority [REDACTED]). [REDACTED] will take all reasonable steps to ensure that specific lens-related information is not passed on to study participants unless this is required for clinical management of an adverse event. Personal subject information will not be made available. To cater for this, subjects will only be referred by their unique identity number in the study report. [REDACTED]

[REDACTED]

[REDACTED]

2.12 Study monitoring

In order to provide quality control and quality assurance as part of this work, the study monitor will:

1. Liaise closely with the Principal Investigator.
2. Monitor and ensure the safety of the subjects.
3. Ensure that the investigation is being conducted according to the protocol.
4. Monitor and review (or oversee review of) the study records to ensure accuracy.
5. Document their observations and make them available to relevant authorised parties [REDACTED]
6. Implement [REDACTED] clinical monitoring standard operating procedure.

Section 3. Subject management

3.1 Visit scheduling

Subjects will be required to attend three visits – an initial/dispensing visit, and two follow-up visits. Follow-up visits will take place after two weeks of contact lens wear for each lens type. Acceptable date ranges are shown in Table 3.

Visit	Target	Allowable range
Initial/Dispensing 1	N/A	N/A
Follow-up 1/Dispensing 2	14 days from Dispensing 1	10-18 days from Dispensing 1
Follow-up 2/ Exit	14 days from Dispensing 2	10-18 days from Dispensing 2

Table 3: Visits and allowable ranges.

3.1.1 Unscheduled visits

Subjects who attend at their own volition, (or as instructed to do so by the investigator) rather than for a scheduled study visit, will be examined and the visit will be classified as 'unscheduled'. Data collected at these visits will be recorded on the clinical study database.

3.1.2 Missed visits

Subjects not attending for a visit will be contacted and encouraged to return for assessment. If two consecutive study visits are missed, the subject will be discontinued. It is expected that [REDACTED] personnel will attempt all reasonable means of communication in this event, including corresponding with the subject by letter.

3.2 Visit conduct

3.2.1 Pre-enrolment

The subject will receive a study-specific information form outlining the study at least 24 hours before the Initial visit.

At a time to suit themselves, each subject will be asked to watch a short on-line information presentation detailing study visits and procedures. They will be asked to complete multiple-choice questions to gauge their understanding of the study. Upon successful completion of these questions, an email is sent automatically to [REDACTED], and the subject is contacted to arrange their initial visit.

3.2.2 Initial/Dispensing 1 visit

Subjects should attend this visit wearing their spectacles. They will be required to sign an informed consent form prior to enrolment (Appendix C). A copy of the signed form will be issued to the subject. When the subject has signed the consent form, they are considered to be enrolled on the study.

Subjects will be instructed on the following:

- ∞ Lens handling, application and removal, where necessary.
- ∞ Specific study instructions, such as the importance of not using any other contact lens products.
- ∞ General contact lens information such as the management of red eyes.

The following procedures will be performed (any ocular measurement procedures outlined below will be carried out on each eye):

1. Details of the ocular history and contact lens wearing history of the subject will be noted (including habitual lenses, modality, wear time today. Average wear time and comfortable wear time over the last two weeks).
2. Subject iris colour will be recorded.
3. Auto-keratometry measures will be recorded.
4. The investigator will perform refraction and high illumination distance and near (40cm) logMAR visual acuity (binocular and monocular, high and low contrast for both distances), in accordance with the current [REDACTED] Standard Operating Procedure 'The set up, measurement of visual acuity and procedures for carrying out an over refraction using the [REDACTED] computerised logMAR VA chart'.
5. The optimal (habitual) reading distance will be recorded and binocular high contrast visual acuity at high illumination will be recorded using a near logMAR chart. The range of clear near vision will also be recorded.
6. Low illumination (100-120 lux) near visual acuity at 40 cm will be recorded as well as the range of clear vision.

7. [REDACTED]
[REDACTED]
[REDACTED]
[REDACTED]
[REDACTED]

11. [REDACTED]
[REDACTED]
[REDACTED]
[REDACTED]
[REDACTED]
[REDACTED]
[REDACTED]

Classification	Primary signs	Secondary signs
[Redacted]	[Redacted]	[Redacted]

[Redacted]

The presence of any adverse events will be recorded [Redacted]

12. The investigator will confirm that the subject satisfies all the inclusion and exclusion criteria. Subjects who fail to meet all the criteria at this time will usually be discontinued and replaced.
13. The first lens pair will be fitted according to the randomisation table [Redacted] and in accordance to the manufacturer's fitting guide. The subject will be masked from the lens type, but will apply the lenses themselves without taking note of the position of any visible markings.
14. Lens rotation and stability will be observed after one, three and 10 minutes of lens settling. Nasal lens rotation is recorded as a positive number and temporal rotation is recorded as a negative number. Following the final 10 minute recording, overall stability will be graded using the grading scales [Redacted]
15. The visibility of the toric markings will be graded after the three minute toric lens fit recording using the grading scales [Redacted]. The investigator will be encouraged to make comments on the visibility in addition to grading.

[Redacted]

[Redacted]

[Redacted]

[Redacted]

[Redacted]

[Redacted]

17. Following the last 10 minute toric fit recording, lens fit will then be assessed using the following evaluations: horizontal and vertical centration, corneal coverage and movement. Normally, for an acceptable fit, centration and movement will fall within currently accepted clinical criteria [between -1 and +1 on a -2 to +2 grading scale

[Redacted]

[Redacted]

18. [REDACTED]
19. An overall grade for lens fit acceptance will be provided for both general lens fit and toric lens fit measures using the grading scales [REDACTED].
20. High illumination, high contrast distance monocular and binocular visual acuity will be recorded using distance logMAR charts before and after spherical over-refraction.
21. High illumination, high contrast near monocular and binocular visual acuity will be recorded at 40 cm using near logMAR charts.
22. High illumination, high contrast near binocular visual acuity will be recorded at the optimal reading distance using near logMAR charts (without over-refraction). The range of clear near vision will also be recorded.
23. [REDACTED]
[REDACTED]
[REDACTED]
[REDACTED]
[REDACTED]
[REDACTED]
[REDACTED]
[REDACTED]
[REDACTED]
[REDACTED]
[REDACTED]
26. The lens care system will be explained and dispensed.
27. The subject will be asked to return two weeks later having worn lenses for a minimum of six hours and five days a week.

3.2.3 Two-week follow-up/dispensing 2 visit

Subjects should attend wearing the study lenses which should have been in situ for at least two hours. Subjects who attend without lenses in situ for at least two hours will usually be rescheduled. The following procedures will be performed:

1. Lens wearing time on study visit day will be recorded.
2. Any study products relating to the previous two weeks of the study will be collected.
3. Details of the contact lens wear since the previous visit will be recorded (including wear time and comfortable wear time).
4. The subject will be asked to score the following with reference to appropriate visual analogue scales (0-100) as outlined in the 'Subjective ratings' document in [REDACTED]
[REDACTED]

[REDACTED]

[REDACTED]

- ∞ Overall comfort
- ∞ Dryness during the day

[REDACTED]

- ∞ Visual fluctuation/stability

[REDACTED]

[REDACTED]

- ∞ Overall handling
- ∞ Overall satisfaction
- ∞ Distance vision
- ∞ Intermediate vision
- ∞ Near vision
- ∞ Near vision in dim illumination

- ∞ Ghosting at distance

- ∞ Ghosting at near

- ∞ [REDACTED]

- ∞ Vision whilst driving during the day

- ∞ Vision whilst driving at night

- ∞ [REDACTED]

[REDACTED]

[REDACTED]

[REDACTED]

[REDACTED]

[REDACTED]

[REDACTED]

[REDACTED]

[REDACTED]

[REDACTED]

[REDACTED]

[REDACTED]

[REDACTED]

[REDACTED]

[REDACTED]

- 6. High illumination, high and low contrast distance and near (40 cm) monocular and binocular visual acuity will be recorded using distance and near logMAR charts before over-refraction. The range of clear vision at near (binocularly) will also be recorded for high contrast measures.
- 7. High illumination, binocular high contrast near visual acuity will be recorded at the subject's habitual working distance (which was recorded at the initial visit) using a near logMAR chart.
- 8. Spherical over-refraction will be performed on each eye if binocular distance high contrast visual acuity is less than 0.2. High illumination, high and low contrast distance and near (40 cm) monocular and binocular visual acuity will be recorded using distance and near logMAR charts. The range of clear vision at near (binocularly) will also be recorded for high contrast measures.

[REDACTED]

[REDACTED]

[REDACTED]

- 11. Lens rotation and stability will be recorded.
- 12. Lens fit and surface will be recorded as described in Section 3.2.1.

[REDACTED]

[REDACTED]

[REDACTED]

- 15. An overall grade for lens fit acceptance will be provided for both general lens fit and toric lens fit measures using the grading scales [REDACTED].

[REDACTED]

[REDACTED]

[REDACTED]

[REDACTED]

[REDACTED]

[REDACTED]

[REDACTED]

[REDACTED]

[REDACTED]

[REDACTED]

[REDACTED]

[REDACTED]

[REDACTED]

[REDACTED]

[REDACTED]

[REDACTED]

[REDACTED]

[REDACTED]

[REDACTED]

[REDACTED]

[REDACTED]

[REDACTED]

18. The lenses will then be removed and discarded.
19. Slit lamp biomicroscopy will be carried out, as detailed in section 3.2.1. The presence of any adverse events will be recorded [REDACTED]
20. The second lens pair will be applied (according to the randomisation table). The subject will be masked from the lens type, but will apply the lenses themselves without taking note of the position of any visible markings.
21. The steps outlined in Section 3.2.1, 13-25 will be repeated.
22. A new bottle of solution and a new case will be issued.
23. The subject will be discharged and asked to return for the four-week follow-up visit. Subjects should be asked to wear their lenses for a minimum of six hours per day, five days per week and to have worn lenses for at least two hours prior to attending the next scheduled visit.

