1.4 Study design

This will be a randomised, subject-masked, crossover, bilateral study, controlled by cross-comparison. Thirty subjects will use each lens type for two weeks in random sequence. Follow-up visits for each lens will be performed after two weeks of wear. Lenses will be worn on a daily wear basis.

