1.5 Statistical considerations

The principal hypothesis to be tested in this work is that subjective scores and visual acuity for the lenses will be substantially equivalent.

[REDACTED]

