1.5.1 Power analysis

In order to determine the study sample size, power analysis was employed using subjective vision data from a previous clinical study. In order to achieve 80% power to detect a difference of 10 units for subjective vision (assuming an alpha of 0.05 and two-tailed paired analysis), 16 completing subjects are required. In order to achieve 80% power to detect a difference of half a line on a LogMAR chart (assuming an alpha of 0.05 and two-tailed paired analysis), 22 completing subjects are required. To allow for discontinuations, 30 subjects will be recruited.

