3.2.4 Four week follow-up/exit visit

Subjects should attend wearing the study lenses which should have been in situ for at least two hours. Subjects who attend without lenses in situ for at least two hours will usually be rescheduled.

The same procedures as at the two week follow-up (Section 3.2.3) will be carried out except that no more lenses will be dispensed. The following additional procedures will be carried out:

[REDACTED]

[REDACTED]

[REDACTED]

[REDACTED]

[REDACTED]

[REDACTED]

[REDACTED]

[REDACTED]

[REDACTED]

[REDACTED]

[REDACTED]

[REDACTED]

[REDACTED]

[REDACTED]

[REDACTED]

[REDACTED]

[REDACTED]

[REDACTED]

[REDACTED]

[REDACTED]

[REDACTED]

[REDACTED]

[REDACTED]

[REDACTED]

[REDACTED]

[REDACTED]

[REDACTED]

[REDACTED]

[REDACTED]

[REDACTED]

[REDACTED]

[REDACTED]

6. On the final visit (or when the subject is discontinued at an earlier visit), the subject will sign a study exit statement acknowledging that the work is complete, although they may have been asked by the investigator to attend a post-study follow-up visit, and that they should continue to use their lenses and solutions as advised, and seek aftercare for their contact lenses. A copy of this signed form will be issued to the subject.
7. The subject will be issued with their payment and all study products will be collected.

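### Follow-up visits set only a two-hour minimum of lens wear and do not match a subject's two visits on hours in situ, so the paired comparison carries avoidable noise and possible bias in either direction (minor)

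*Combined protocol and SAP*

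**What the plan says.** Section 2.6.1.1 gives the general rule: "The lenses should also be worn for a minimum of two hours before attending the follow-up visits". Section 3.2.3 repeats it for the two-week visit ("Subjects should attend wearing the study lenses which should have been in situ for at least two hours") and enforces it: "Subjects who attend without lenses in situ for at least two hours will usually be rescheduled". Section 3.2.4 states the same floor for the exit visit and adds: "The same procedures as at the two week follow-up (Section 3.2.3) will be carried out except that no more lenses will be dispensed".

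Step 1 of 3.2.3 reads "Lens wearing time on study visit day will be recorded", so the hours in situ are captured at both follow-ups. Table 3 in 3.1 controls the day of each visit (10 to 18 days from dispensing) but not the hour. No visible text sets a target or maximum wear time, matches a subject's two visits, or says how the recorded wearing time will be used.

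On design and analysis, section 1.4 says "Thirty subjects will use each lens type for two weeks in random sequence". Section 1.5 says "The principal hypothesis to be tested in this work is that subjective scores and visual acuity for the lenses will be substantially equivalent", and the text after that sentence is redacted. Section 1.5.1 gives 22 completers for "80% power to detect a difference of half a line on a LogMAR chart", with two-tailed alpha 0.05 and a paired analysis, and plans to recruit 30.

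**The concern.** Each lens has one two-week follow-up. Low contrast acuity with the lens on appears, in the visible text, only there, and so do acuity, rotation and fit after two weeks of wear. If these measures change over a day's wear, hours in situ form part of what is compared.

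The protocol itself treats hours in situ as relevant: it sets a minimum, usually reschedules subjects below it, and records the value. It does not ask for the two values to be alike within a subject. One lens could be seen shortly after the two-hour mark and the other late in the wearing day.

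Two consequences need to be kept apart. If the mismatch is unrelated to lens, it widens the paired differences and costs power. If it follows the lens, for example because a less comfortable lens is inserted later, it shifts the mean difference. Randomising the order balances period, not behaviour that the lens itself causes.

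**Working it through.** **Inputs from the documents (1.5.1).** 22 completers, half a line, 80% power, two-tailed alpha 0.05, paired analysis, 30 recruited. No SD is given.

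**Assumptions.** One logMAR line is 0.1, so half a line is 0.05. Acuity drift with wear is b = 0.005, 0.010 or 0.015 logMAR per hour. The within-subject difference in visit-day wear time has an SD of 3 hours. None of these is in the documents.

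**Step 1: the plan's own figure.** Without an SD, the 22 cannot be reproduced independently, but the SD it implies can be solved for. Paired-t power is P(T > t(0.975, n−1)), with T noncentral t on n−1 degrees of freedom and noncentrality 0.05·√n/SD. Setting power to 80% gives SD = 0.0778 at n = 21 and 0.0798 at n = 22. A requirement of 22 therefore implies an SD between these values, and 0.0798 is used below. At that SD, 30 completers give 91.2% power.

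**Step 2: mismatch unrelated to lens.** SD_total = √(0.0798² + (3b)²).

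| Drift b per hour | 3b | SD_total | Power, n = 22 | Power, n = 30 | n for 80% |
|---|---|---|---|---|---|
| 0 | 0 | 0.0798 | 80.0% | 91.2% | 22 |
| 0.005 | 0.015 | 0.0812 | 78.6% | 90.3% | 23 |
| 0.010 | 0.030 | 0.0853 | 74.6% | 87.4% | 25 |
| 0.015 | 0.045 | 0.0916 | 68.5% | 82.3% | 29 |

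The mean is not affected. In a simulation with b = 0.010, a wear-time-difference SD of 4.24 hours and a true difference of 0.05, the average estimate was 0.050.

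**Step 3: mismatch that follows the lens.** Observed difference = true difference ± b × mean wear-time difference. Take an assumed mean of 2 hours and b of 0.005 to 0.010, so the shift is 0.005 × 2 = 0.01 to 0.010 × 2 = 0.02.

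- If the lens with worse acuity is worn for less time, 0.05 appears as 0.04 to 0.03, and power at 22 is 61.1% to 39.1%.
- If the lens with better acuity is worn for less time, 0.05 appears as 0.06 to 0.07, and power at 22 is 91.9% to 97.5%.

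Nothing in the documents says which case is the more likely.

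**The case against.** The strongest objection is that the SD in Step 1 is back-solved from a sample size based on earlier data, and nothing says wear time was matched in that earlier study. If it was not, 0.0798 already contains this noise and Step 2 counts it twice; the loss against plan could then be nil. This stands, and it makes the Step 2 losses an upper bound for the assumed drifts.

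The drift and the spread of hours are also assumed. At 0.005 logMAR per hour the cost is about 1.4 percentage points at 22, and 30 completers keep power above 80% in every noise-only row. This also stands.

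There are partial safeguards. Visit-day wearing time is recorded, so an imbalance can be seen. High contrast distance and near acuity is also measured at each dispensing (3.2.2, steps 20 to 22, repeated for the second lens under 3.2.3, step 21), after the 10-minute fit readings and so at similar settling times. That comparison is useful, but it is not two-week data, and its visible steps do not cover low contrast.

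A reader might infer that the loose rule pulls the result towards the equivalence the trial hopes to show. The documents do not support that, for two reasons:

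- The inference needs the less comfortable lens also to be the one with worse acuity. If it has the better acuity, the same behaviour enlarges the difference.
- Noise helps an equivalence claim only if a non-significant test is read as equivalence. With a margin and a confidence interval, noise makes equivalence harder to show: for an assumed 0.05 margin and no true difference, TOST power at 22 falls from 76.9% to 69.0% at 0.010 logMAR per hour. No decision rule is visible, and part of section 1.5 is redacted.

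**Conclusion.** The gap is real: there is a two-hour floor only, and no visible matching of a subject's two follow-ups on time of day or hours in situ. The consequence is an avoidable source of noise and a possible bias of unknown sign. Its size cannot be derived from the documents. Under the stated assumptions the noise costs between 1.4 and 11.5 percentage points of power at 22 completers (80% less 78.6% and 68.5%) and leaves at least 82.3% at 30. The cost is smaller or nil if the earlier SD already reflected unmatched wear. Randomised order does not protect against a lens-dependent mismatch, but no direction can be claimed for it. The point is minor and worth acting on because the remedy is cheap.

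**What to change.** In 3.2.3 and 3.2.4, leave the two-hour minimum as it is and add one sentence: each subject's two follow-ups are booked at a similar time of day, and the subject is asked to insert the lenses at a similar time on both visit days.

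In the analysis section, state that visit-day wearing time will be reported by lens. Pre-specify a supportive analysis of all pairs that regresses the paired difference (test minus control) on the wear-time difference, so that the intercept estimates the lens difference at equal wear. Label it supportive, because wear time is observed after randomisation and may itself respond to the lens.

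Do not restrict the analysis to subjects with matching wear times. That selects on a post-randomisation variable. With a 3-hour SD centred on zero, a 2-hour window would keep only 2Φ(2/3) − 1 = 49.5% of subjects, or about 11 of 22, with about 47% power for 0.05 logMAR at an SD of 0.0798.

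The cost is slightly less freedom in booking the second follow-up, plus one table and one model from data already collected. No visit, procedure or subject is added.

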2.1.3 Inclusion criteria

Subjects will only be eligible for the study if:

1. They are aged 40 - 70 years, inclusive.
2. They understand their rights as a research subject and are willing and able to sign a Statement of Informed Consent.
3. They are willing and able to follow the protocol.
4. They have successfully completed the non-dispensing study (C16-597) as the lenses to be worn on this study (C16-599) are predetermined from their participation on study C16-597.
5. They have a contact lens spherical prescription between +10.00 to -10.00D (inclusive).
6. They have astigmatism between of -0.75 and -5.75DC (based on the calculated ocular refraction) in each eye.
7. They have an Add component to their spectacle refraction (between +0.75 and +2.50DS).
8. They can be satisfactorily fitted with the study lenses.

9. They can attain at least 0.30 logMAR binocular distance high contrast visual acuity with the study lenses within the available power range.
10. They have successfully worn soft contact lenses in the last two years.
11. They are willing to comply with the wear schedule (at least five days per week and for at least six hours per day).
12. They agree not to participate in other clinical research for the duration of this study.
13. They own a wearable pair of spectacles.

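### Does the follow-up over-refraction trigger of 0.2, written without a unit or a better-or-worse direction, undermine the acuity comparison?

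*Combined protocol and SAP*

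**What the plan says.** The trigger is in step 8 of section 3.2.3: "Spherical over-refraction will be performed on each eye if binocular distance high contrast visual acuity is less than 0.2". Its second sentence then calls for a set of high and low contrast acuities at distance and near, on logMAR charts. Section 3.2.4 applies the same rule at exit: "The same procedures as at the two week follow-up (Section 3.2.3) will be carried out except that no more lenses will be dispensed".

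Four other places bear on how to read it:

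- Step 6 of section 3.2.3, two steps earlier, has no condition: "visual acuity will be recorded using distance and near logMAR charts before over-refraction".
- Inclusion criterion 9 in section 2.1.3 is the only other visible acuity threshold, and it names its unit: "They can attain at least 0.30 logMAR binocular distance high contrast visual acuity".
- At dispensing, step 20 of section 3.2.2 has no trigger: "High illumination, high contrast distance monocular and binocular visual acuity will be recorded using distance logMAR charts before and after spherical over-refraction". Step 21 of section 3.2.3 repeats this for the second lens pair: "The steps outlined in Section 3.2.1, 13-25 will be repeated". The section number cited there is a slip, since the numbered steps are in 3.2.2.
- Step 4 of section 3.2.2 cites an operating procedure whose title covers "measurement of visual acuity and procedures for carrying out an over refraction using the" site's computerised chart. That procedure is not among the documents.

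**The concern.** LogMAR runs backwards: 0.10 is better than 0.20. Taken as a number, a value below 0.2 picks out the subjects who see well and leaves out those at 0.20 or poorer, where over-refraction would help explain the result. Taken in the ordinary sense of acuity falling short of a standard, the same words pick out the opposite group. The sentence has neither a unit nor the words better or worse, and step 8 does not itself refer to the operating procedure.

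Visual acuity is part of the principal hypothesis in section 1.5. If two examiners read the rule differently, or one examiner read it differently at the two visits, over-refracted acuity after two weeks of wear would exist for a haphazard subset that might not be comparable between lenses. If those values fed the main comparison, this would be a real defect.

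**Working it through.** The plan states no figure for this rule, so there is none to reproduce. The check has four parts.

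**1. Unit.** Steps 6 and 7 and the second sentence of step 8 all record acuity on logMAR charts. The alternative, decimal acuity, can be tested with logMAR = -log10(decimal): -log10(0.2) = 0.70. That is far poorer than the 0.30 logMAR entry limit and would trigger almost nobody. LogMAR is the only workable unit.

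**2. Direction.** Let x be binocular distance high contrast acuity in logMAR.

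- Literal reading: trigger if x < 0.20 (better acuity).
- Ordinary-sense reading: trigger if x > 0.20 (poorer acuity).

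The sets are disjoint and agree only at x = 0.20, where neither triggers. Now apply the same two readings to criterion 9. Literally, it would require x ≥ 0.30 and admit only subjects at 0.30 or poorer, which makes no sense as an entry standard. It must mean x ≤ 0.30. The protocol therefore speaks of acuity by quality, not by numerical value, and in that usage *less than 0.2* is x > 0.20. The usual purpose of over-refraction, finding out why acuity is reduced, points the same way.

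**3. How far the readings differ.** The documents give no acuity distribution. Assume a normal distribution with mean m from -0.10 to +0.10 and SD s from 0.08 to 0.15 logMAR. The share selected literally is Φ((0.20 - m)/s); the other reading takes the rest.

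| m | s | (0.20 - m)/s | Literal reading | Ordinary sense |
|---|---|---|---|---|
| -0.10 | 0.08 | 3.75 | 1.000 (30.0 of 30) | 0.000 (0.0 of 30) |
| 0.00 | 0.10 | 2.00 | 0.977 (29.3 of 30) | 0.023 (0.7 of 30) |
| 0.10 | 0.15 | 0.67 | 0.748 (22.4 of 30) | 0.252 (7.6 of 30) |

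Over this range the literal reading makes follow-up over-refraction close to universal, an odd result for a step written as an exception. If the mean were as poor as 0.20, the split would be 15 and 15 by symmetry.

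**4. What the triggered data feed.** At follow-up, subjective scores are taken at step 4 and as-worn acuity at step 6, both before step 8, so over-refraction cannot alter either. Step 18 then discards the lenses, and nothing in the visible text makes the over-refraction change what is worn. The objectives (1.3), the hypothesis (1.5) and the power statement (1.5.1, which aims to "detect a difference of half a line on a LogMAR chart" in a paired analysis) do not mention over-refracted follow-up acuity.

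Three figures look like a size for the problem and are not:

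- 30 subjects × 2 follow-ups = 60 assessments that change status. Reversing any threshold changes every value not equal to it.
- The repeat set has 2 contrasts × 2 distances × 3 viewing conditions = 12 values, of which step 20 supplies 3 at dispensing. Setting 12 - 3 = 9 mixes fitting-day values with values after two weeks of wear.
- The band from 0.20 to 0.30 is 0.10 logMAR wide, twice half a line if a line is 0.10. One is an eligibility range and the other a mean paired difference, so the ratio has no meaning.

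**The case for a change.** The best case for acting is that the sentence is not determinate as written, that the fix is a few words, and that over-refracted acuity after two weeks of wear can separate residual spherical error from lens performance. Dispensing data do not replace it, because they come from the fitting day and, in the visible steps, cover only high contrast distance acuity after over-refraction. The operating procedure may settle the direction, but a reader of the protocol cannot confirm that.

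Some of this stands. The sentence would be clearer with its unit and an explicit direction, and the sponsor may add them if the text is being revised anyway. The intended direction is for the sponsor to confirm.

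The step from loose wording to a flaw in the analysis does not stand. Under either reading, the trigger depends on acuity with the lens being worn, so the over-refracted subset is selected on an outcome after randomisation. It would not support a fair comparison between lenses even if the rule were worded perfectly, so clearer wording gains nothing for inference. Section 3.4 already has the report show how many subjects enter each analysis, so a partial set would be visible. Nor can a sentence naming the step 6 values be called missing: the text directly after the hypothesis in section 1.5 is redacted and may already specify the analysis.

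**Conclusion.** No change is needed. This is a drafting slip in a step that yields ancillary data. The unit is clear from the neighbouring steps. The direction is not stated, but criterion 9's usage and the purpose of over-refraction both point to poorer acuity. The readings could differ by most of the sample in who is over-refracted at follow-up (about 22 to 30 against 0 to 8 of 30 under the assumed distributions), yet the effect on the as-worn acuity comparison is zero, because step 6 records acuity for every subject on each lens before the trigger applies.

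This rests on two assumptions: that the principal acuity comparison uses the step 6 values, the natural choice since they alone are untriggered at follow-up, and that no redacted passage gives the triggered values a formal role. Nothing in the visible text suggests otherwise.
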